### **Study visits and procedures:**

Study procedures that can be done remotely will be conducted via video visit to minimize patient contact and provide scheduling flexibility to participants.

1. **Screening visit (-2 weeks)\*\*:** At the screening visit participants will undergo the following procedures.
  - a. Informed consent
  - b. Collection of demographic and disease characteristics
  - c. Collection of concomitant medication information
  - d. Vital signs, physical and neurological examination\*
  - e. Verification of eligibility based on inclusion/ exclusion criteria
  - f. Venipuncture for baseline safety laboratory testing\*
  - g. MSFC\* and MSQOL-54 assessments
  - h. Urine pregnancy test\*
  - i. Suicidality evaluation (C-SSRS)

If the participant is eligible for the trial, they will then return for the baseline visit at which time they will be randomized to a treatment group and begin the trial.

2. **Baseline visit (0 weeks)\*\*:**

Following procedures will occur at this visit:

- a. Screening laboratory tests will be reviewed to assess whether there is any contraindication for continuation in trial
- b. Update concomitant medication information

- c. Update medical and disease history
- d. Vital signs, physical and neurological information\*
- e. Venipuncture for PBMCs and safety laboratory tests\*
- f. Stool specimen collection
- g. MSFC\*, MSQOL-54 and Food frequency questionnaire assessments
- h. EDSS evaluation\*
- i. Urine pregnancy test\*
- j. Suicidality evaluation

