**4. End-of-study visit (16 weeks)**

The following procedures will occur at this study visit.

- a. Assessment of adverse effects
- b. Review of safety labs
- c. Update medical and disease history
- d. Update concomitant medication information
- e. Vital signs, physical and neurological examination\*
- f. Venipuncture for PBMCs and safety labs\*
- g. Stool specimen collection
- h. MSFC\*, MSQOL-54 and Food frequency questionnaire assessments
- i. EDSS evaluation\*
- j. Urine pregnancy test\*
- k. Suicidality evaluation

\*Must be done at in-person portion of visit

\*\* Due to the COVID-19 pandemic and to make it more convenient for the patients to participate, we decided to offer the option of three visits instead of four as an alternative. In this case, we will perform the research blood draw and stool sample at the screening visit, along with providing patients with medicine. We will ask patients not to start taking medicine until we receive the screening lab results and let them know whether they are eligible and can start the medication.

Study procedure	Screening	Baseline Week 0	Week 8	Week 16
Written consent	X			
Verify eligibility	X			
Medical history, relapse assessment	X	X	X	X
Medication review (also antibiotic and probiotic use)	X	X	X	X
Vital signs, physical, neurologic (EDSS) exams*	X	X	X	X
MS Functional Composite* & MSQOL-54	X	X	X	X
Adverse event assessment		X	X	X
Food frequency questionnaire		X	X	X
Laboratory testing (CBC, CMP, HbA1c, Lipid profile, pregnancy test)*	X	X	X	X
Blood for PBMC isolation* & Stool specimen collection		X	X	X
Suicidality evaluation (C-SSRS)	X	X	X	X

\*Must be done at in-person portion of visit

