**c. Statistical plan including sample size justification and interim data analysis.**

Safety data will be analyzed as they are captured in real time. Assessments will focus on AEs (including study treatment tolerability assessments, laboratory evaluations, vital signs and physical examination). The incidence rate of AEs will be recorded by system organ class, severity and by relationship to study treatment. Tolerability analysis will be based on the number (%) of participants who failed to complete the study due to adverse events. Lab values for each parameter will be summarized by shift tables. For quantitative parameters, we will present summary statistics for actual values and change from baseline. We will compare changes over the 16-week treatment period between the groups using mixed effects regression analyses to account for repeated measures using random subject-specific intercepts and slopes.

Metabolomics data will be analyzed at the end of the study following quantitation of the 15 bile acids included in our panel. Summary statistics will be used to characterize these outcomes. We will then assess normality of these measures and perform appropriate univariate testing to determine which bile acids are significantly altered by TUDCA supplementation. A mixed effects longitudinal model will also be used to test which bile acids are altered between visits across the two groups. Models will also adjust for important covariates including BMI, age, gender and measures derived from the food frequency questionnaire.

Gut microbiota data, *a priori* analyses will assess changes in relative abundances of different gut bacteria as well as microbial genes that encode bile acid metabolizing enzymes (identified from the literature and NCBI Gene database) which occur as a result of TUDCA treatment. Exploratory analysis will assess the effects of TUDCA on the metagenome using a combination of pathway and set-based approaches previously applied in metagenomics analysis of MS and other diseases to identify other biologically relevant changes[41]–[43].

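### The between-arm model for quantitative safety measures states no use of pre-dose values as an adjustment, although two are collected on the four-visit route

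*Combined protocol and SAP*

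**What the plan says.** The relevant text is in sections 4a, 7b and 7c of the combined protocol and SAP.

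- **Schedule.** Section 4a lists "Venipuncture for baseline safety laboratory testing" at screening (two weeks before week 0) and "Venipuncture for PBMCs and safety laboratory tests" at the baseline visit. The schedule table marks laboratory testing (CBC, CMP, HbA1c, lipids) and the row "Vital signs, physical, neurologic (EDSS) exams" at screening, week 0, week 8 and week 16. MSFC and MSQOL-54 are marked at the same four visits.
- **Three-visit route.** A note to the schedule says "we decided to offer the option of three visits instead of four as an alternative". Research samples and drug supply then move to screening, so these participants may have only one pre-dose value. Expected uptake is not given.
- **Descriptive analysis.** Section 7c: "For quantitative parameters, we will present summary statistics for actual values and change from baseline".
- **Between-arm analysis.** Section 7c: "We will compare changes over the 16-week treatment period between the groups using mixed effects regression analyses to account for repeated measures". The model gives each participant a random intercept and a random slope. No pre-dose covariate is named. The bile-acid models in the same section do list covariates (BMI, age, gender, diet measures).

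Section 7c does not define baseline. Section 4a leaves the term open, because the screening blood draw is itself labelled baseline testing while week 0 is the baseline visit.

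**The concern.** This mixed model is the only inferential between-arm comparison that 7c names for safety. Adverse events and tolerability are given as rates and percentages, and labs are also given as shift tables. With 30 per arm, the width of the interval decides how much a finding of little difference in a liver or kidney measure can tell the reader.

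As worded, the model appears to start at week 0 and to treat that value as one more outcome. If each arm has its own free mean at week 0, all the measurement noise of that one reading passes into the estimate of change. Both pre-dose values precede treatment, so in a randomised comparison they can be used to reduce that noise without biasing the between-arm contrast. The data are already scheduled, so the precision costs nothing extra to collect.

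**Working it through.** **1. Is there a plan figure to reproduce?** Not for this contrast. Section 7c gives no SD, correlation or power for any safety parameter. Its sample size rests on bile acids: 27 / (1 - 0.10) = 30 per arm, which reproduces and does not depend on this point.

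**2. What the planned model estimates.** Visits are at weeks 0, 8 and 16, equally spaced. With complete data, linear time, random intercept and slope, independent residuals and a free arm difference at week 0, the generalised least squares weights for the 16-week change are (-1, 0, +1). I checked this numerically for three sets of variance components. Each participant contributes week 16 minus week 0, and week 8 has no weight.

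**3. Variance formulas.** Take variance 1 at each visit, correlation ρ between any pre-dose value and week 16, and correlation ρs between screening and week 0. Both are assumptions.

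- Change from one value: 2(1 - ρ)
- Adjustment for one pre-dose value: 1 - ρ²
- Adjustment for the mean of two: 1 - 2ρ²/(1 + ρs)

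For an effect that the change contrast detects with 80% power (two-sided 0.05), power becomes Φ(2.80 × √(variance ratio) - 1.96), where 2.80 = 1.96 + 0.84 and the ratio is the change variance divided by the adjusted variance.

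**4. Worked case, ρ = ρs = 0.5.** Variances are 1.00, 0.75 and 1 - 0.5/1.5 = 0.667. Ratios to the change contrast are 1.333 and 1.50. Power is Φ(2.80 × 1.155 - 1.96) = 90% with one value and Φ(2.80 × 1.225 - 1.96) = 93% with two.

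**5. Range.**

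| ρ | ρs | Change | One value | Two values | Power, one | Power, two | Points from screening |
|---|---|---|---|---|---|---|---|
| 0.5 | 0.5 | 1.00 | 0.75 | 0.67 | 90% | 93% | 3.1 |
| 0.7 | 0.7 | 0.60 | 0.51 | 0.42 | 86% | 92% | 5.6 |
| 0.9 | 0.9 | 0.20 | 0.19 | 0.15 | 82% | 90% | 8.4 |
| 0.5 | 0.8 | 1.00 | 0.75 | 0.72 | 90% | 91% | 1.0 |
| 0.7 | 0.9 | 0.60 | 0.51 | 0.48 | 86% | 88% | 1.7 |
| 0.9 | 0.95 | 0.20 | 0.19 | 0.17 | 82% | 86% | 4.1 |

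At ρ = 0.5 most of the gain comes from adjusting at all. At ρ = 0.9 most of it comes from the second pre-dose value.

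**6. Cross-check in the planned type of model.** With 27 per arm, ρ from 0.5 to 0.9 and a random-slope SD of 0 to 0.5 baseline SDs per 16 weeks (again assumed), entering screening as a second pre-dose record at time 0 lowers the standard error of the arm-by-time slope by 6.3% to 14.7% if arms differ freely at baseline, and by 5.4% to 13.4% if they share one baseline mean.

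All figures assume that every participant has two pre-dose values. The screening share shrinks as three-visit uptake rises.

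**The case against.** The strongest reply is that 7c specifies a repeated-measures mixed model, and that change from baseline appears only in the sentence on descriptive summaries. The plan does not say how time or arm is coded. If the arms were given a common mean at week 0, the model would already use that value much as a covariate adjustment does. This stands: step 2 is conditional on complete data, linear time and a free arm difference, and the text neither states nor excludes a common mean.

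A reader might go further and infer that the plan discards the screening values. The documents do not say so. The reference to the treatment period makes exclusion likely, but a mixed model can accept another pre-dose record.

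A reader might also extend the point to MSFC and MSQOL-54. No model is named for them, and the quoted sentence sits in the safety paragraph. Nor can two pre-dose values be assumed for lipids and HbA1c: section 7b places them at baseline and end of study, while the schedule table marks all four visits.

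Two further points are fair. Little rests on this analysis: the primary outcome is adverse events and drop-out, and individual labs are also watched through shift tables and the thresholds in 7d. And because screening labs are reviewed before a participant continues, averaging them into descriptive changes could bring regression to the mean into within-arm summaries. That argues for leaving the tables on week 0, not against adjusting the between-arm contrast.

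**Conclusion.** The point holds as a minor, inexpensive improvement. For CBC, CMP and vital signs, section 7c states neither adjustment for pre-dose values nor a common pre-dose mean, and probably leaves screening out. Read literally, the contrast carries the full noise of one week-0 reading.

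Under the assumed equal correlations, using both pre-dose values would move a contrast from 80% power to about 90% to 93%. It would be wrong to credit all of that to the screening value: its own share is about 3 to 8 points, or about 1 to 4 if readings two weeks apart agree more closely than readings 16 weeks apart, which is plausible. The plan supplies no correlation from which to choose within these ranges. The primary outcome and the sample size do not change.

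**What to change.** Add to section 7c, in words such as: *Between-arm comparisons of post-dose quantitative safety parameters adjust for the pre-dose value, defined as the mean of screening and week 0 where both exist and otherwise the single pre-dose value; alternatively, all pre-dose values enter the mixed model with one common pre-dose mean for both arms.* Choose one of the two forms before unblinding.

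Also:

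- State that descriptive change-from-baseline tables use week 0, or the single pre-dose value on the three-visit route.
- If MSFC and MSQOL-54 are to be compared between arms, name the model and apply the same rule.
- Reconcile 7b with the schedule table on the timing of lipids and HbA1c before assuming two pre-dose values for them.

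The cost is a few sentences and no new data. The one drawback is that three-visit participants have a slightly noisier baseline.

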**3. Mid-study visit (8 weeks)**

The following procedures will occur at this study visit.

- a. Assessment of adverse effects
- b. Review safety labs
- c. Update medical and disease history
- d. Update concomitant medication information
- e. Vital signs, physical and neurological examination\*
- f. Venipuncture for PBMCs and safety labs\*
- g. Stool specimen collection
- h. MSFC\*, MSQOL-54 and Food frequency questionnaire assessments
- i. EDSS evaluation\*
- j. Urine pregnancy test\*
- k. Suicidality evaluation

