## 7. Study Statistics

**a. Primary outcome variable.**

The primary outcome of this study is the safety and tolerability of TUDCA supplementation. This will be based on number of adverse events occurring in the two treatment groups and the rate of drop-out in each study arm. This data will be documented at each study visit.

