### b. Steps taken to minimize the risks.

TUDCA treatment: We are utilizing a dose of TUDCA that has recently been shown to be safe in a trial in another chronic neurological disorder. We are also monitoring safety labs and conducting neurological evaluations every 8 weeks to monitor for any adverse effects that may be related to the treatment.

Venipuncture: Blood will be drawn by a trained study team member.

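### The only named between-arm model for quantitative safety parameters uses subject-specific slopes and no by-visit contrast; read as a straight line, it cannot test a week-8 shift that resolves by week 16

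*Combined protocol and SAP*

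**What the plan says.** For quantitative safety parameters, section 7c of the combined protocol and SAP states: "We will compare changes over the 16-week treatment period between the groups". The method is "mixed effects regression analyses to account for repeated measures using random subject-specific intercepts and slopes". The section does not say whether the fixed effect of time is linear or by visit, which contrast is tested, or whether the screening value is used.

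Under the study visits and schedule table in section 4a, safety blood is drawn at screening two weeks before baseline ("Venipuncture for baseline safety laboratory testing"), at baseline (week 0), at the mid-study visit (week 8) and at the end-of-study visit (week 16). Section 8b confirms the on-treatment interval: "We are also monitoring safety labs and conducting neurological evaluations every 8 weeks". Week 8 is therefore the only scheduled on-treatment draw before the end.

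This model is not the primary analysis. On the primary outcome, section 7a says: "This will be based on number of adverse events occurring in the two treatment groups and the rate of drop-out in each study arm". Section 7c also plans adverse-event incidence tables, laboratory shift tables, summaries of values and of change from baseline, and real-time review. Section 7d sets individual laboratory limits for stopping treatment and a monitoring board that meets every 12 weeks.

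**The concern.** A random slope varies around a mean slope, so the usual companion fixed effect is linear time with a group-by-time interaction. With three equally spaced visits, that interaction reduces to the end-to-start change. The middle visit, half of the scheduled on-treatment laboratory data, drops out of the tested contrast.

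At stake is a mean shift in, say, a liver test that appears by week 8 and settles by week 16 while most individual values stay inside the stopping limits. The one formal comparison named for these parameters would not register it.

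A smaller concern arises when an effect reaches its plateau by week 8. A participant whose last value is at week 8 then shows twice the true 16-week slope, so missing week-16 values pull the estimate upwards. Such gaps are to be expected: section 7c assumes 10% drop-out, and section 4f removes participants whose safety laboratory values become abnormal.

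**Working it through.** **Inputs from the document.** Visits at weeks 0, 8 and 16 (section 4a); two-sided alpha 0.05, an upper requirement of 27 per arm, 10% drop-out and 30 recruited per arm (section 7c). The plan's own figure reproduces: 27 / (1 - 0.10) = 30. I use 27 per arm for power.

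**Inputs assumed.** The document gives no variance components. I took intercept variance 0.6, slope variance 0.0005 or 0.001 per week squared (intercept-slope covariance 0 or -0.005 respectively), and residual variance 0.2 or 0.4: four sets in all.

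**Slope weights.** The least-squares slope weight at time t is (t - mean) / sum of (t - mean)^2. The mean time is 8 and the sum of squares is 64 + 0 + 64 = 128, so the weights are -8/128, 0 and +8/128, or (-1, 0, +1)/16. Generalised least squares gives the same weights under all four sets. A week-8-only shift contributes nothing to the slope difference, so the rejection rate is 5% whatever its size.

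**Week-8 contrast with visit as a category.** For change from baseline, SE = sqrt(2v/27), with v = Var(week 0) + Var(week 8) - 2 Cov. Power is approximately Phi(shift/SE - 1.96).
- Most favourable set: v = 0.432 and SE = 0.179. The week-8 SD is 0.912, so a 0.75 SD shift is 0.684; 0.684/0.179 = 3.82 and power is 97%.
- Least favourable set: v = 0.864 and SE = 0.253. The week-8 SD is 0.992, so the shift is 0.744; 0.744/0.253 = 2.94 and power is 84%.

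| Week-8 shift, gone by week 16 | Straight-line slope test | Week-8 contrast |
|---|---|---|
| 0.5 SD | 5% | 50-72% |
| 0.75 SD | 5% | 84-97% |
| 1 SD | 5% | 97-99.9% |

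**When the zero weight fails.**
- Adding the week -2 screening value gives week 8 a slope weight of 0.0123 per week, against 0.0517 for week 16.
- A common baseline intercept gives week 8 a weight of 0.005 to 0.011 per week; power for a 0.75 SD shift is then 6 to 8%.
- A joint test of intercept and slope has 13 to 15% power at 0.75 SD.
- With 10% of one arm missing week 16, a 1-unit week-8 shift moves the estimated 16-week change by 0.06 to 0.07 units.

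**Plateau effect with drop-out.** Suppose a true difference of 0.80 at both weeks 8 and 16, with 10% of the TUDCA arm lacking week 16 independently of outcome. The straight-line model then has expectation 0.82 to 0.83 across the four sets. For scale, with SD 0.95, r = 0.5 and 27 per arm, the SE is 0.95 x sqrt(2/27) = 0.26, so an excess of about 0.03 is roughly a tenth of an SE.

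**Precision at week 16.** Under compound symmetry with correlation r, the per-subject variance (in units of the outcome variance) is 2(1 - r) for the slope contrast and 1 - r^2 for the baseline-adjusted week-16 value. The ratio is 2/(1 + r): 1.43 at r = 0.4, 1.33 at 0.5 and 1.18 at 0.7. The gain comes from baseline adjustment, not from treating visit as a category.

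**The case against.** The strongest reply is that the plan specifies random slopes and says nothing about the fixed effect of time. Random slopes can be combined with visit as a category, and week 8 is then estimated directly. This stands: the straight-line mean is an inference, though the natural one. It leaves two possibilities, a linear model that is blind to a transient week-8 effect or an unspecified model, and the same wording resolves both.

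A reader might also infer that a week-8 safety signal would go undetected in the trial. The document does not support that. The primary outcome is adverse events and drop-out. Week-8 blood results are reviewed, individual limits stop treatment, and the shift tables and change-from-baseline summaries can display the signal. What remains is narrower: those tables are descriptive and the limits act on individuals, so none is a planned between-arm test of a mean shift.

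Three further inferences should be resisted:
- Zero weight is not general. The working shows where it fails, although none of those variants amounts to a proper week-8 test.
- Setting the slope against an average of weeks 8 and 16 would suggest a larger loss of precision, but that average is a different quantity from the per-visit differences recommended here.
- The criticism does not carry over to bile acids. Section 7c describes their longitudinal model separately and mentions no random slopes.

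**Conclusion.** The concern holds for the formal between-arm comparison of quantitative safety parameters. Read as a straight line, with complete data at the three visits and arm-specific intercepts, that comparison has alpha-level power for a transient week-8 shift, where a by-visit contrast would have good power for shifts of 0.75 SD or more. The zero weight is exact under those conditions; the power figures depend on assumed variances. The drop-out bias is real in direction but modest at the planned 10%. The point concerns specification and efficiency. It leaves the primary adverse-event and drop-out analysis and the individual safety monitoring intact, but the change is worth making because it uses data already being collected.

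**What to change.** In section 7c, for quantitative safety parameters, replace the random-slope model with a repeated-measures model. Include the baseline value as covariate, treatment, visit (weeks 8 and 16 as categories) and treatment-by-visit, with unstructured covariance over the two post-baseline visits. Report the TUDCA minus placebo difference with 95% CI at each visit. State which measurement serves as baseline, given the screening draw and the three-visit option.

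The cost is SAP wording only, with no added visits or samples. The downsides are two contrasts per parameter instead of one slope and slightly more parameters. Participants with no post-baseline value do not contribute to the comparison.

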## PRELIMINARY DATA

**People with MS have alterations in their metabolome compared to healthy controls.** We performed untargeted global metabolomic profiling of plasma from people with RRMS and healthy controls (n=27 in each group) utilizing gas or liquid chromatography coupled with tandem mass spectrometry. The mass spectra obtained were compared to a reference library to identify individual compounds and the relative abundance was calculated using the area under the curve of the mass spectra. Using this method, we identified over 600 metabolites in the plasma of study participants and were able to differentiate the two groups based on their metabolic profiles using a statistical model optimized for high-dimensional datasets - orthogonal partial least squares -discriminant analysis (OPLS-DA) (Figure 2).

[figure not shown]
**People with MS have alterations in both primary and secondary bile acid metabolism.** In the first discovery cohort described above we noted reductions in the levels of multiple primary and secondary bile acids in people with MS. To follow-up on our findings, we performed untargeted metabolomics in a validation cohort of 50 RRMS, 50 progressive MS and 50 healthy controls. In this study we again noted a reduction in multiple bile acids in RRMS and PMS groups (Figure 3A). We also investigated alterations in individual metabolic pathways using pathway dysregulation scores (calculated as described in Drier et al)[28]. This method generates a score for a metabolic pathway for each individual based on their distance from a principal components curve constructed based on healthy control data. These scores range from 0 to 1 with higher scores representing greater abnormality in the pathway. We found significant alterations in both primary and secondary bile acid metabolism in RRMS and PMS groups (Figure 3B & 3C). In this cohort, we also noted a correlation of PDS scores for secondary bile acid metabolism with those for xenobiotic

[figure not shown]
**Figure 2. Metabolomics differentiates people with MS from healthy controls.** The plot depicts the first two components from an orthogonal partial least squares -discriminant analysis (OPLS-DA) model. The two groups can be clearly distinguished in this plot.

metabolism (Xanthine and Benzoate,  $p < 0.01$  for both) indicative of a link between the gut microbiota and bile acid metabolism.

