#### Sample size justification

Since this is primarily a safety study we based our sample size on the ability to detect changes in our secondary outcomes, especially metabolomics. Previous studies of supplementation of UDCA and TUDCA have resulted in alterations in the total serum bile acid levels (2-8 fold change) and the composition of the bile acid pool. Based on our preliminary data, to detect a 50 - 70% change in levels of an individual bile acid, with a power of 85% and two-tailed alpha of 0.05 the required sample size would be between 14 – 27 in each arm. Accounting for a 10% drop-out rate, we will aim to recruit 30 participants in each arm of the trial. We have previously noted significant alterations in metabolic profiles in MS patients treated with vitamin D and dimethyl fumarate in studies utilizing between 18-24 patients (as shown in preliminary data).

From a safety stand-point, a sample size of 30 would enable us to conclude with 80% confidence that the rate of occurrence of serious adverse events with TUDCA treatment was less than 5% if none of the patients experienced a serious adverse event during the study[40].

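### Section 7c does not say how the pre-dose bile acid level enters the arm comparison; specifying baseline adjustment would gain precision at almost no cost

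*Combined protocol and SAP*

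**What the plan says.** Section 7c gives two analyses for the panel of 15 bile acids. The first is a univariate test, chosen after normality has been checked; whether it uses follow-up values, changes or within-person pairs is not stated. The second is longitudinal: "A mixed effects longitudinal model will also be used to test which bile acids are altered between visits across the two groups". On covariates it adds: "Models will also adjust for important covariates including BMI, age, gender and measures derived from the food frequency questionnaire". The pre-dose bile acid level is not in that list, and nothing is said about whether the two arms share one baseline mean.

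Section 7b provides for plasma to be stored before and after treatment, so each participant's pre-dose level will be available.

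The sample size rests on this outcome. The Sample size justification reads: "Based on our preliminary data, to detect a 50 - 70% change in levels of an individual bile acid", and continues "with a power of 85% and two-tailed alpha of 0.05 the required sample size would be between 14 – 27 in each arm". After allowance for 10% drop-out, 30 per arm are to be recruited. The SD, its type (cross-sectional or of change), the correlation r and the test assumed are not given.

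**The concern.** A model that compares changes between visits, with a separate baseline mean for each arm, behaves like a comparison of change scores. That subtracts the whole baseline difference, which over-corrects unless r is 1. A test of follow-up values alone makes no correction. Using the pre-dose value as a covariate, or constraining the arms to one pre-dose mean (which randomisation justifies), applies the right amount of correction. Apart from one degree of freedom, it is never less efficient than either alternative.

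At stake is the precision of the comparison on which the sample size was built. The bile acid work in the Preliminary data is a set of group comparisons: 27 people with RRMS against 27 controls, and then "we performed untargeted metabolomics in a validation cohort of 50 RRMS, 50 progressive MS and 50 healthy controls". The planning SD may therefore be a one-time, between-person SD. If it is, and r is below 0.5, a change-type analysis is noisier than the calculation assumed.

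**Working it through.** **Inputs from the documents.** Two-sided alpha 0.05; power 85%; effect 50% to 70% of one bile acid; 14 to 27 per arm; 10% drop-out; 30 per arm recruited (all from the Sample size justification).

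**Inputs assumed.** r is not given, so a range is shown. The SD is not given, so it is solved from the plan's own figures. Variances are taken as equal before and during treatment, and r as the same in both arms. One baseline and one follow-up value are used.

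**Step 1: the plan's figure.** For two independent means, n per arm = 2 × [(1.960 + 1.036) × SD / effect]².

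- Solving for the SD: 0.613 of the mean from (50%, n = 27) and 0.618 from (70%, n = 14).
- One SD of 0.61 returns both ends: 2 × (2.996 × 0.61/0.50)² = 26.7, so 27; and 2 × (2.996 × 0.61/0.70)² = 13.6, so 14.
- Drop-out: 27/(1 − 0.10) = 30.
- Log-scale versions do not fit both ends (27 and 16 for increases, 28 and 9 for decreases).

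The stated range is therefore consistent with an ordinary two-group comparison with SD 0.61. Because the SD was solved from the range, this is not an independent confirmation, and it does not show which kind of SD was used.

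**Step 2: variance multipliers on SD², if the SD is cross-sectional.**

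- Follow-up only: 1
- Change score, or free baseline means: 2(1 − r)
- ANCOVA, or common baseline mean: 1 − r²

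The ratio of the second to the third is 2(1 − r)/[(1 − r)(1 + r)] = 2/(1 + r).

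**Step 3: power at 27 per arm, SD 0.61.** Power = Φ(effect / [SD × √multiplier × √(2/27)] − 1.960).

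Example at r = 0.3, effect 50%, with √(2/27) = 0.272:

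- Change-type: SE = 0.61 × √1.4 × 0.272 = 0.196; 0.50/0.196 − 1.960 = 0.585; power 72.1%.
- Adjusted: SE = 0.61 × √0.91 × 0.272 = 0.158; 0.50/0.158 − 1.960 = 1.197; power 88.4%.

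| r | Variance ratio 2/(1+r) | Change-type, 50% effect | Adjusted, 50% effect | Change-type, 70% effect |
|---|---|---|---|---|
| 0 | 2.00 | 56.7% | 85.4% | 84.6% |
| 0.2 | 1.67 | 66.3% | 86.7% | 91.5% |
| 0.3 | 1.54 | 72.1% | 88.4% | 94.6% |
| 0.4 | 1.43 | 78.5% | 90.8% | 97.1% |
| 0.5 | 1.33 | 85.4% | 93.5% | 98.8% |
| 0.7 | 1.18 | 97.3% | 98.8% | above 99.9% |

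A follow-up-only test has 85.4% for the 50% effect at any r. Repeating the 50% calculation with the noncentral t and SD 0.60 gives almost the same values (71.9% and 88.3% at r = 0.3). If a week 8 sample is also assayed, then under compound symmetry the week 16 contrast has the same powers: 72.1% against 88.4% at r = 0.3, and 85.4% against 93.5% at r = 0.5.

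**Step 4: if 0.61 was already the SD of change (50% effect, 27 per arm).**

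| r | Change-type | Adjusted | Follow-up only |
|---|---|---|---|
| 0.3 | 85.4% | 96.2% | 94.6% |
| 0.5 | 85.4% | 93.5% | 85.4% |
| 0.7 | 85.4% | 90.4% | 64.5% |

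The adjusted analysis stays at or above about 85% in every case examined. Each of the others drops below it in some case.

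**The case against.** A reader might infer that the plan ignores the pre-dose level and throws its information away. The text does not support that. The covariate list is open-ended, and a longitudinal model across visits would normally carry the pre-dose value as a repeated response, possibly with a common mean. The plan neither states nor excludes this. What can be said is that the handling is unspecified.

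A reader might also infer that the trial is underpowered. That does not follow either:

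- **SD type.** The Sample size justification refers only to preliminary data. The bile acid comparisons there are cross-sectional, but the same section reports a before-and-after vitamin D metabolomics study with 24 people with MS. That study reports no bile acid results, so the type of SD stays open. If it was an SD of change, a change-type analysis keeps its 85%.
- **Correlation.** No r is given. At 0.5 or above there is no shortfall in the change-type analysis.
- **Effect size.** At a 70% change with 27 per arm, change-type power is 84.6% at r = 0 and at least 88% from r = 0.1.
- **Expected effects.** The plan cites 2- to 8-fold changes from earlier studies. On the same SD a 100% change gives about 99% power even at r = 0. Those figures are for total serum bile acids, however, and individual acids may move less.
- **Idealised variances.** A drug expected to raise bile acids may alter the on-treatment variance and the correlation in one arm, so the powers above are illustrative.

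All of these points stand, and they limit the claim about power. They do not remove the case for specifying the adjustment. Carrying baseline as a response with free arm means still has the 2/(1 + r) variance, and not knowing r or the SD type favours the method that holds up under either.

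**Conclusion.** The point holds as a gain in efficiency that the plan leaves unclaimed. Section 7c specifies neither a pre-dose covariate nor a common baseline mean. If the arm comparison is run on change scores or with free baseline means, its variance is 1.54 times the adjusted variance at r = 0.3 and 1.33 times at r = 0.5, assuming equal variances and the same correlation in both arms.

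For that form of analysis, a fall below 85% power for a 50% change at 27 per arm requires a cross-sectional planning SD and r below 0.5. The documents establish neither, so the loss is possible but not shown. Nor is this a question of bias: under randomisation the free-baseline and common-baseline analyses are both unbiased, and the choice affects precision only. Bile acids are a secondary outcome; the primary assessment of safety and tolerability is unaffected.

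**What to change.** In Section 7c, state that each bile acid is compared between arms at week 16 with its pre-dose value as a covariate (ANCOVA). Alternatively, specify a longitudinal model with one pre-dose mean common to both arms and visit-specific arm contrasts. Either should take the place of the unadjusted univariate test. In the Sample size justification, add the SD behind 14 to 27 per arm, whether it is cross-sectional or of change, and the correlation assumed, if any.

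The cost is a sentence or two of SAP wording and one degree of freedom in the analysis. The plan already calls for the pre-dose sample, so no participants, visits or assays are added.
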